Secondary Efficacy Endpoints

- Phase I:
 - Improvement in WOMAC scores between all study time points – pre-treatment and following 3 months and 6 months post-treatment;
 - Improvement in Visual Analog Score (VAS) score between all study time points;
 - Improvement in Short-Form 36 (SF-36) score between all study time points;
 - Reduction in usage of pain killers or NSAIDS
- Phase II:
 - Original Active group - Improvement in knee pain and knee function scores, as measured by change from baseline WOMAC score to 12 months post treatment;
 - Original Active group - Improvement in VAS score between baseline and 12 months post treatment;
 - Original Active group - Improvement in SF-36 score between baseline and 12 months post treatment;
 - Original Active group - Reduction in usage of pain killers or NSAIDS
 - Cross-over group - Improvement in WOMAC scores between all study time points – pre-treatment and following, 3 months and 6 months post-treatment;
 - Cross-over group - Improvement in Visual Analog Score (VAS) score between all study time points;
 - Cross-over group - Improvement in Short-Form 36 (SF-36) score between all study time points
 - Cross-over group - Reduction in usage of pain killers or NSAIDS

CONFIDENTIAL

This material is the property of the NYU School of Medicine and Langone Medical Center. Do not disclose or use except as authorized in writing by the study sponsor

Outcome Measure Evaluation Criteria

Western Ontario and Mac Master University (WOMAC) – the WOMAC is a self-administered osteoarthritis outcomes instrument designed to assess lower extremity pain and function in osteoarthritis of the knee or hip. The minimal clinically important difference (MCID) proportion is a 16.0% reduction in WOMAC [Hmamouch, 2014].

Visual Analog Score (VAS) Scale - the VAS is a validated pain scale that asks subjects to rate the amount of pain they are currently experiencing on a line up to 100mm (no pain is equal to 0mm and the worst imaginable pain is equal to 100mm). An improvement of 20 points from the baseline score is considered a statistically significant improvement at that visit [Gallagher, 2001].

Short-Form (36) Health Survey – the SF-36 is a patient reported survey of health that is designed to measure health status. The survey consists of eight (8) sections, where the lower the score the more disability and the higher the score the less disability [Maruish, 2009].

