During the baseline visit, the Apostherapy® team will meet with the patient to set them up with their device. Utilizing state-of-the-art technology, an in-depth analysis consisting of step length; load distribution on each leg; walking velocity; and gait symmetry, will be obtained. A personally-calibrated device will not be used for patients randomized to this group. The patient will receive a sham-placebo foot-worn biomechanical device. During their daily routine, patients will be asked to wear their custom-worn device for approximately 2 hours per day, up until the 6 month follow-up visit, starting with less than an hour of walking around the house and gradually increasing wearing time to outdoor walking. Patients will be asked to come to follow-up visits at the treatment center (located at [name]) at the following time points: 3 -4 weeks, 7 weeks, 12 weeks, 18 weeks, 24 weeks, 27 weeks, 36 weeks, 42 weeks and 52 weeks. During these visits the biomechanical device will be adapted according to the clinical needs of the patient (this will have no actual effect on the biomechanical device, since there are no biomechanical element in the sham device).

Phase I Study Visits

Patients will be followed for 6 months after enrollment. Patients will be seen for a screening/baseline visit and will then return to NYULMC (the physician's office) for a follow-up visit at, 3 months and 6 months from initial visit.

VISIT 1/2 - Screening/Baseline visit (the screening/baseline assessments may be completed in more than one session):

The following procedures will be conducted at the physician's office located at NYULMC Center for Musculoskeletal Care, [name]:

- Sign Informed Consent Document;
- Review Inclusion/Exclusion Criteria;
- Randomize patient to one of two study arms;
- Review and document demographics, medical/surgical/concomitant medication history (complete data collection form);
- Physical Knee Evaluation (will include the following, but not limited to):
 - Pain: Note location and activities that increase and decrease symptoms, joint line tenderness, etc.
 - Knee Effusion: Presence or absence

CONFIDENTIAL

This material is the property of the NYU School of Medicine and Langone Medical Center. Do not disclose or use except as authorized in writing by the study sponsor

- Ligament Stability: Anterior drawer test, posterior drawer test, lachman test, pivot shift, valgus/varus stress test.

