This material is the property of the NYU School of Medicine and Langone Medical Center. Do not disclose or use except as authorized in writing by the study sponsor

Data Analysis

Phase I:

- Primary outcome measures will include comparing scores at baseline and the following study time points (baseline, 3 months and 6 months) obtained from the WOMAC. The WOMAC is a validated outcomes assessment used to measure patients' opinion about their knee and associated problems.
- Secondary outcome measures will include comparisons of all measured variables between baseline and all time points including VAS score, SF-36 score, improvement and maintenance in knee function using physical examination findings (these include, but are not limited to: Pain, Knee Effusion, Ligament Stability, Stability, Strength, Range of Motion, Sensation, Posture/alignment); and monitoring usage of rescue medications or NSAIDs. All data will be obtained from the completed case report forms that are being utilized for this study.

Phase II:

- Original active group – evaluating the changes in pain, function, quality of life and usage of rescue medications or NSAIDs following 12 months of therapy.
- Cross-over group – comparing scores at baseline and the following study time points (baseline, 3 months and 6 months) obtained from the WOMAC, SF-36, knee function and usage of rescue medications or NSAIDs.

DATA SAFETY MONITORING PLAN (DSMP)

I. Study Monitoring

The principal investigator, [name], will be the data safety monitor for this project. After a three (3) months follow-up period, [name] will review the data for SAE's, protocol deviations and other issues. If it is determined that certain events occur above an expected rate (i.e. increased knee pain), then enrollment will be stopped.

II. Types of Data

Under this DSMP, the following data/events will be captured and documented:

- Duration of AposTherapy® use;
- Monitoring of patient falls;
- Patient Outcomes Assessments;
- Reportable and/or adverse events
- Protocol Deviations

III. Responsibilities and roles for gathering, evaluating and monitoring the data:

Principal Investigator

After a three (3) months follow-up period, the PI will meet with any co-investigators and the Research Coordinator to discuss the current findings and analysis. During these meetings, the PI will also be responsible for verifying data accuracy, and compliance with the study protocol.

Research Coordinator

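### The Phase I secondary analysis is wider than the endpoint list and framed against baseline rather than sham, and the cross-over analysis leaves out VAS, a listed endpoint

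*Combined protocol and SAP*

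**What the plan says.** **Endpoint list.** Secondary Efficacy Endpoints gives four kinds of endpoint for Phase I. The first is "Improvement in WOMAC scores between all study time points – pre-treatment and following 3 months and 6 months post-treatment". The others are VAS and SF-36, each compared across the visits, and a reduction in analgesic use. No physical-examination finding is listed. The cross-over group in Phase II has the same four kinds, among them "Cross-over group - Improvement in Visual Analog Score (VAS) score between all study time points".

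**SF-36.** Outcome Measure Evaluation Criteria notes that "The survey consists of eight (8) sections". No section or summary score is chosen; both the endpoint list and the analysis text speak only of an SF-36 score.

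**Phase I analysis.** Data Analysis places WOMAC at 3 and 6 months in its primary bullet. Its secondary bullet calls for "comparisons of all measured variables between baseline and all time points including VAS score, SF-36 score, improvement and maintenance in knee function". Knee function there is taken from the physical examination, with findings introduced as "these include, but are not limited to: Pain, Knee Effusion, Ligament Stability, Stability, Strength, Range of Motion, Sensation, Posture/alignment". The examination is open-ended at the visits too: "Physical Knee Evaluation (will include the following, but not limited to". Use of rescue medication or NSAIDs is to be monitored.

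**Cross-over analysis.** The Phase II bullet compares scores "obtained from the WOMAC, SF-36, knee function and usage of rescue medications or NSAIDs". VAS is not named. The visit descriptions collect it at weeks 24, 36 and 52, and the Phase II text makes the 6-month results this group's new baseline.

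**Error control.** The only test and significance level are in the sample size text (Study Summary and Sample Size Analysis): a two-sided t-test on pain score at 0.05. For the secondary outcomes the plan gives no test, hierarchy, multiplicity adjustment or statement that they are exploratory.

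**The concern.** The endpoint list and the analysis section describe different sets of secondary outcomes, and no text says which governs. The choice of what counts as a secondary result could therefore be made after the data are seen.

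Two routes to a misleading claim follow from the Phase I wording. First, the stated comparison is with baseline, with no between-arm contrast. Patients enter on a pain threshold (VAS of at least 3), so regression to the mean and placebo response can produce real improvement within either arm. Reported as written, that improvement could be presented as efficacy of the device. Second, an open list of variables examined at each visit gives chance more opportunities, and nothing in the plan limits which nominally significant results may be claimed.

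The cross-over bullet raises a different problem. A listed endpoint has no stated analysis, while knee function appears beside WOMAC without a definition. The primary endpoint is not affected by any of this.

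**Working it through.** **1. The two lists side by side**

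| Outcome | Listed secondary, Phase I | In Phase I analysis | Listed secondary, cross-over | In cross-over analysis |
|---|---|---|---|---|
| WOMAC | yes | yes (primary bullet) | yes | yes |
| VAS | yes | yes | yes | **not named** |
| SF-36 | yes | yes | yes | yes |
| Analgesic use | yes | yes | yes | yes |
| Knee-examination findings | no | **yes, open list** | no | **unclear (knee function)** |

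In Phase I the discrepancy is addition: every listed item is covered. In the cross-over group there is one omission and one undefined term. The Phase II primary endpoints measure knee function by WOMAC for this same group, whereas the Phase I secondary bullet uses the term for examination findings.

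**2. How far the additions could matter**

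The plan gives no error rate for secondary outcomes, so there is no figure to reproduce on this point. (Its one related figure, 80% power for pain score, comes out at about 99% with 60 per arm at 0.8 SD; that is a separate matter.)

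Assumptions, none of them stated in the documents for secondary outcomes:
- each comparison is tested at two-sided 0.05;
- every null hypothesis is true, which suits an active-versus-sham contrast rather than change from baseline;
- each named examination domain counts as one variable;
- there are two follow-up visits (months 3 and 6);
- WOMAC is left out, because the analysis section treats it as primary.

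Number of tests, k:
- VAS, SF-36 as one score, medication use: 3 × 2 = 6
- adding the eight named domains: (3 + 8) × 2 = 22
- also counting SF-36 as eight sections: (1 + 8 + 8 + 1) × 2 = 36

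Expected false positives are 0.05 × k, whatever the correlation. Under independence, the chance of at least one is 1 − 0.95^k. For correlated tests, equicorrelated normal statistics were simulated (100,000 runs).

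| k | Expected false positives | Independent | Correlation 0.3 | 0.5 | 0.7 |
|---|---|---|---|---|---|
| 6 | 0.3 | 26% | 24% | 21% | 16% |
| 22 | 1.1 | 68% | 57% | 44% | 30% |
| 36 | 1.8 | 84% | 71% | 55% | 36% |

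Moving from the listed items to those named in the analysis section (6 to 22) roughly doubles the chance of a false positive at each correlation shown.

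**3. What closing the list would leave**

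VAS, one SF-36 score and medication use at month 6 only are 3 tests: 1 − 0.95³ = 14% under independence. An order or an exploratory label is therefore still needed.

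**The case against.** The strongest reply is that this is loose drafting. The primary objective and its hypothesis set the calibrated device against sham, and the sample size assumes a two-sample test, so a between-arm comparison may be understood throughout. Secondary results are often read as exploratory. The cross-over VAS endpoint is itself prespecified with its time points, and the schedule collects secondary variables at the relevant weeks. The examination findings are standard clinical observations that may never be tested.

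Part of this stands. Several stronger readings that a reader might infer are not supported:

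- **That the analysis section ignores the listed Phase I endpoints.** It names all four kinds.
- **That 36 tests is a minimum, or 84% the trial's error rate.** Both the endpoint list and the analysis text refer to an SF-36 score, and nothing says eight sections will be tested. Medication use is described as monitoring. The 84% also needs independence, which is implausible for repeated measurements on the same patients and largely the same knee, and a 0.05 level that the plan does not set for secondaries.
- **That leaving out VAS produces chance findings.** Omitting a variable adds no false positives. It looks like a drafting slip, and the documents give no sign of an intention to withhold it.
- **That knee function in the cross-over bullet is a new examination endpoint.** The term is undefined there and could mean WOMAC function.

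What the reply does not remove is the text itself. The section is titled as efficacy endpoints, nothing calls them exploratory, the only stated secondary comparison in Phase I is with baseline, and the two lists conflict without a rule of precedence.

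**Conclusion.** The point holds as an inconsistency that should be corrected; it does not threaten the primary analysis. The missing active-versus-sham contrast is the more serious part, because improvement within an arm can be real and still say nothing about the device. The open list comes second: under the assumptions above, the chance of at least one false positive goes from 16–26% to 30–68% once the eight named domains are added, and to 36–84% if SF-36 is also split into eight sections. These ranges run from correlation 0.7 to independence. They illustrate scale and do not predict the trial's error rate: the true number of comparisons is unknown because the list is open, and could be larger. The cross-over VAS gap is a separate mismatch between endpoint and analysis.

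**What to change.** Reword the Data Analysis section, and align the endpoint list with it:

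- Make the Secondary Efficacy Endpoints list the complete secondary efficacy set.
- For Phase I, define each secondary comparison as active versus sham in change from baseline at month 6.
- Name one SF-36 score as the endpoint.
- Report month-3 results, the other SF-36 sections and the knee-examination findings as descriptive estimates with 95% confidence intervals and no significance claims.
- For the remaining secondaries, either fix a testing order or label them exploratory. Either would do; the choice is the sponsor's.
- Add VAS to the cross-over analysis, and state that function there means WOMAC function.

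This needs no new data, visits or patients. The cost is that fewer secondary results can be called significant.
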